5.9 Description of available data

[figure not shown]
Descriptive statistics for continuous variables such as age (in years) will be done using relevant measure of central tendency (mean) and measures of spread (standard deviation) of the data accounting for clustering. For continuous variables which are normally distributed, we will report the means and standard deviations adjusted for clustering. For example, on the variables age or blood pressure levels; we can report the mean ± standard deviation when data are normal. Apart from presenting these measures, data will also be presented graphically using some of the following: histograms, box and whisker plots, lowess plots, scatter plots and kernel density plots.

Categorical variables such as gender will be described through frequency tabulations by reporting the number of observations and missing values, where necessary, for instance on gender: male (n, %), female (n, %). Bar charts and pie charts will also be used to give

visual descriptive of the categorical variables. We will estimate population prevalence by standardizing this to the Agincourt age groups distribution.

5.10 Flow Diagram for Trial

The following figure shows the schematic view of the data flow and randomised between the control and intervention cluster arms.

5.11 Representativeness of sample

For each of the two population surveys, we intended to select a random sample of 5000 people aged over 18 years from the demographic surveillance database. The baseline survey has been completed, with a sample of 4903 persons and a response of 3905 (79.6%). The samples for the two surveys will be disproportionately stratified to ensure adequate representation of males and older people. This is necessary because the population pyramid is heavily weighted to younger people and there are fewer men than women amongst older adults due to labour migration ^{8,9}. The samples will be a fair representation of the resident adult population in Agincourt at both the baseline and end of intervention visit. Because labour migrants are living away most of the time and are not available for interview (and only rarely use local primary care services) they are not

included in the surveys. Those individuals that are identified as labour migrants in the census database will not be selected for the surveys, but there will be some people who have become labour migrants since the last census update, and these people will inevitably be missed in the survey.

5.12 Baseline comparability of randomized groups

Once the database is complete with data from both population surveys entered, we will compare the respondents' characteristics by randomised group and by individual clinic to assess the comparability of the groups. We want to ensure that individuals in the control and intervention clusters are similar by describing their socio-demographic factors; these will be described for both the baseline and the follow-up survey. If similar, this will strengthen our findings to the extent that other factors constant, we can attribute differences after 24 months to the intervention strategies in place. We will also compare with the intervention and control group those individuals surveyed who did not attend a participating clinic – we expect these numbers to be small.

6 ANALYSIS OF PRIMARY OUTCOME

6.1 Definition of outcome measure

The primary outcome will be the change in the percentage of people in the population who have elevated blood pressure that is combined with other factors resulting in a risk profile that indicates moderate or greater added risk of cardiovascular disease. as indicated by the shaded cells in Table 2. This includes individuals with either: a systolic blood pressure of 160 and above, diastolic of 100 and above, systolic blood pressure of 140-159 plus one or more risk factors, or diastolic blood pressure 90-99 plus one or more risk factors. These data will be obtained from two population surveys (one before the start of the trial and one after the trial ends).

Table 2. Modified South African Guideline: Stratification of cardiovascular risk in patients with hypertension (defined as SBP>139 or DBP>89)

Blood pressure (mmHg)	Presence of risk factors or other conditions						
	No risk factors	One or two risk factors	Three or more risk factors or diabetes	Associated clinical conditions			
SBP 140 -159 or DBP 90-99	Low Added Risk	Moderate Added Risk	High Added Risk	Very High Added Risk			
SBP 160 -179 or DBP 100-109	Moderate Added Risk	Moderate Added Risk	High Added Risk	Very High Added Risk			
SBP 180 + or DBP 110+	High Added Risk	Very High Added Risk	Very High Added Risk	Very High Added Risk			

6.2 Descriptive statistics for outcome measure

An overall frequency tabulation of the primary outcome cross-classified by group will be produced, based on the study design.

6.3 Primary analysis

The analysis of the primary outcome (binary, as defined above) will be done in three steps Thus, firstly, a group level analysis of the overall effect of the intervention using the test of differences in two proportions (within each group at baseline and after follow-up and between intervention and control clusters) will be conducted adjusting for the design effect and clustering correction factors for each group. We will not use the usual Pearson's Chi-Square test which assumes independence as our data are clustered. Intra-class correlation (ICC) adjusted Pearson's Chi-square versions will be used as those used by Reed. These will involve creating and pilot testing a STATA program to perform these adjusted Chi-Square based analyses for binary outcome data¹⁰⁻¹².

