2.2 Outcome Measures

2.2.1 Primary Outcome

A population level measure of hypertension control will be derived from cross-sectional surveys carried out before and after the intervention. This primary outcome will be the change between the two surveys in the percentage of people in the population who have elevated blood pressure that is combined with other factors resulting in a risk profile that indicates moderate or greater added risk of cardiovascular disease. More detailed definitions of outcomes are described in section 5.7.

2.2.2 Secondary Outcomes

- a) Change in proportion of the population with undiagnosed hypertension (see table 10 in the appendix)
- b) Change in the proportion of the population reporting they had had their blood pressure measured (see table 10 in the appendix),
- c) Change in the proportion of the population reporting that they are using medication for hypertension (see table 10 in the appendix)
- d) Change in the proportion of the population at different levels of blood-pressurerelated cardiovascular risk by age group and sex (see tables 5, 6, 7, 8 and 9 in the appendix)
- e) Change in the proportion of people in the population reporting that they have attended a clinic in the last year (see table 10 in the appendix)
- f) Retention in care of people with diagnosed hypertension defined by the proportion of appointments kept during the study period (see table 11 in the appendix)

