3 STUDY METHODS

3.1 Overall Study Design and Plan

We will conduct a cluster-randomised trial in tandem with a detailed realist evaluation. drawing on global experience of evaluating complex interventions^{1,2}. The units of randomisation will be health facilities and their surrounding catchment populations. We propose to randomise eight clinics, four of which will receive the intervention. To achieve our primary outcome, we aim to both increase the proportion of the population under active management for their hypertension and reduce the level of blood pressure in those patients already receiving care. For this reason, the outcome of the trial will be measured at population level, and we estimate that the trial has a power of above 80% to detect an 11% to 13% reduction in the proportion of the population at moderate or greater cardiovascular risk as a result of their blood pressure and other risk factors. Realist evaluation will provide data on adaption of the intervention to the context, individual and organizational processes of change as well as contextual factors that influence outcomes³. We are collecting data at two cross-sectional points 24 months apart: baseline (when intervention is introduced) and at the end of intervention at each clinic to provide data on the sustainability of the intervention. The detailed study methods are described in the following sections.

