3.5 Sample size determination

The two cross-sectional surveys, which will be used to assess the effectiveness of the intervention, will each include at least 4000 participants, giving approximately 500

people in each cluster. We adopted the use of the coefficient of variation (standard deviation of the cluster means divided by the overall mean) as used in similar study settings when we cannot get a good intra-cluster variation⁴⁻⁶. For a background prevalence of 36% (i.e. proportion of patients at moderate or greater risk of cardiovascular disease) and a coefficient of variation of 0.132 (error margin 4.5% (0.132 ± 0.045)) based on data collected in the same site in 2010, different scenarios of proportions of moderate or greater risk patients at the end of trial in the control and intervention arms and their associated power are shown in Table 1. Based on the scenario of a 15% difference (i.e. 36% in control vs 21% in intervention), the highest power will be 97.4% and we will have power of above 80% to detect an 11% absolute reduction of people at moderate or greater cardiovascular risk. These calculations assume that the coefficient of variation will be similar in the two groups and that effects of the interventions are similar across clusters.

	Control	"36%" No change	
	CV	0.132	
Intervention	"5% difference" 31%	20.7	
	"10% difference" 26%	68.6	
	"12% difference" 24%	85.4	
	"15% difference" 21%	97.4	
	Control	"34%" 2% change	
	CV	0.132	
Intervention	"3% difference" 31%	10.5	
	"8% difference" 26%	52.7	
	"10% difference" 24%	75.4	
	"13% difference" 21%	94.2	
	Control	"32%" 4% change	
	CV	0.132	
Intervention	"1% difference" 31%	4.3	
	"6% difference" 26%	35.2	
	"8% difference" 24%	58.4	
	"11% difference" 21%	87.7	

Table 1: Power	matrix of different scenari	ios
-----------------------	-----------------------------	-----

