5.2 Population Surveys

Two population surveys were carried out (one before the intervention starts and one after it finishes) to estimate the primary outcome of the trial. In each survey, a random sample of 5000 people aged over 18 years were selected from census records, to allow for 20% attrition, so that at least 4000 individuals were included in each survey, contributing approximately 500 people in each of the 8 clusters. From previous experience in this research setting, we expect good participation (~80%). The sample was disproportionately stratified to ensure adequate representation of males and older people. This is necessary because the population pyramid is heavily weighted to younger people and there are fewer men than women amongst older adults due to labour migration.

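### Section 6.3 names no test of the between-arm difference in change, and its between-arm adjusted chi-square with four clinics per arm has a type I error of about 10% or more

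*SAP*

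**What the plan says.** - **Outcome.** SAP 2.2.1: "This primary outcome will be the change between the two surveys in the percentage of people in the population" at moderate or greater added risk. Section 6.1 repeats this as a change.
- **Design.** SAP 3.1: "We propose to randomise eight clinics, four of which will receive the intervention". SAP 5.2 has each survey "contributing approximately 500 people in each of the 8 clusters".
- **Primary analysis.** SAP 6.3 plans a two-proportion test, applied within each arm (baseline against follow-up) and between arms, "adjusting for the design effect and clustering correction factors for each group". It then states: "Intra-class correlation (ICC) adjusted Pearson's Chi-square versions will be used". It announces three steps and describes one. It gives no alpha, reference distribution, degrees of freedom or permutation test.
- **Supporting analyses.** SAP 6.5 lists a two-stage regression ending at clinic level, and a mixed model, under analyses that support the primary one.
- **Reporting.** Dummy Tables 9 and 10 have a final column for a test of the difference between the arms' changes, with a p-value.
- **Power.** SAP 3.5, Table 1 covers "different scenarios of proportions of moderate or greater risk patients at the end of trial in the control and intervention arms", with "a coefficient of variation of 0.132 (error margin 4.5% (0.132 ± 0.045").

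**The concern.** Two separate problems meet in section 6.3.

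**The contrast.** The test named there gives one p-value for change in the intervention arm, one for change in the control arm, and one for intervention against control on a proportion. None says whether the two changes differ. One arm may show a significant change and the other not, without any evidence that the changes differ. With no decisive test fixed, the analyst could choose among these p-values after seeing them.

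**The calibration.** The adjusted chi-square divides the Pearson statistic by an estimated design effect. With four clinics per arm that estimate carries 6 df (3 per arm if done separately). Reading the statistic against chi-square on 1 df treats the estimate as known, which overstates significance in the between-arm comparison.

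**Working it through.** **Inputs.** Four clinics per arm (3.1); m = 500 per clinic (5.2); prevalence 36% and CV 0.132, with limits 0.132 − 0.045 = 0.087 and 0.132 + 0.045 = 0.177 (3.5). Assumed, because not stated: two-sided alpha 0.05, chi-square reference on 1 df, and the correlation of clinic prevalence between surveys.

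**Step 1: the plan's own power figures.** ICC = CV² × p/(1 − p) = 0.017424 × 0.36/0.64 = 0.0098. Design effect = 1 + 499 × 0.0098 = 5.89. For 36% v 26%, deducting one clinic per arm (c − 1 = 3):
- variance = 5.89 × (0.36 × 0.64 + 0.26 × 0.74)/500/3 = 0.00166, so SE = 0.0407
- z = 0.10/0.0407 − 1.96 = 0.49, so power = 68.9%; Table 1 gives 68.6%.

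All 12 cells of Table 1 agree within 1.7 points. A noncentral t on 6 df with 400 per clinic fits about as well (within 1.6 points). Both close fits carry a correction for few clusters. Section 6.3 states none for the test.

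**Step 2: type I error of the between-arm test at one time point.** As a guide, a t statistic on 6 df judged against 1.96 gives P(|t₆| > 1.96) = 9.8%. Null simulation (beta-binomial clinics, 36%, equal clinics of 500, ANOVA ICC, critical value 3.841):

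| CV | Pooled ICC | ICC per arm | t-test on clinic proportions, 6 df |
|---|---|---|---|
| 0.087 | 9.0% | 11.5% | 5.0% |
| 0.132 | 9.6% | 14.3% | 5.0% |
| 0.177 | 9.7% | 15.3% | 5.1% |

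With clinic sizes from 150 to 850 at CV 0.132, the two chi-square versions give 10.2% and 15.7%.

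**Step 3: the within-arm tests.** These treat the two surveys of the same clinics as independent sets of clinics. Null rejection with a pooled ICC is about 9.8%, 4.5% and 1.9% at assumed between-survey correlations of 0, 0.5 and 0.8. The error therefore changes direction as the correlation rises.

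**Step 4: the contrast that is needed.** Applied to the difference in mean clinic change, a 1.96 cut-off rejects 9.7% under the null. The t critical value on 6 df (2.447) rejects 5.0%.

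**Step 5: power of valid tests, 36% v 25%, CV 0.132.** Clinic SD is taken as CV × prevalence.
- *Follow-up proportions, t on 6 df.* Summed variance = (0.2304 + 0.1875)/500 + 0.017424 × (0.1296 + 0.0625) = 0.00418. Noncentrality = 0.11/√(0.00418/4) = 3.40. Power is about 81%.
- *Clinic changes, t on 6 df.* At correlation r, the control-arm variance is 2 × 0.2304/500 + 0.017424 × 2 × 0.1296 × (1 − r). The intervention-arm variance is 0.4179/500 + 0.017424 × (0.1921 − 2r × 0.09).

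| r (assumed) | Summed variance | Noncentrality | Power |
|---|---|---|---|
| 0 | 0.00962 | 2.24 | 47% |
| 0.5 | 0.00579 | 2.89 | 67% |
| 0.8 | 0.00350 | 3.72 | 87% |

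**The case against.** **Part of this is handled elsewhere.** Section 6.5 plans a clinic-level regression and a mixed model, which may be the missing steps, and Tables 9 and 10 show that a between-arm test of change is intended. This stands as mitigation. It would be wrong to say that the authors overlooked the contrast or planned no clinic-level analysis. But 6.5 labels those models supporting and does not say that either one models change, so the primary p-value still has no defined method.

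**The SAP does not say how the statistic is referred.** True. The 1-df reference and two-sided 5% are inferences, though natural ones for a Pearson chi-square on two proportions. If the planned Stata program applied a small-sample reference, the calibration problem would shrink. The missing contrast would remain.

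**A reader might infer a type I error of 15%, or of two to three times nominal without condition.** The text does not support that. The upper end requires the correction factors to use a separate ICC in each arm, and "adjusting for the design effect and clustering correction factors for each group" can equally mean a common ICC with factors that differ through clinic size. One version with arm-specific ICCs and an unpooled z statistic gives only 9.4–9.8%.

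**A reader might also infer that every test in 6.3 is anti-conservative.** Step 3 shows otherwise: the within-arm tests become conservative once clinic prevalences correlate over time.

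**Conclusion.** The point holds in two parts. First, from the text alone: the primary outcome is a change compared between arms, and section 6.3 names no test that delivers that comparison or its confidence interval. Second, conditional on two-sided 5% and chi-square on 1 df: the between-arm test has a type I error of about 10% with a pooled ICC, and about 11–15% with ICCs per arm and equal clinics, across the SAP's own CV range. These rates belong to the between-arm comparison. They are not a single error rate for the trial, because the SAP does not fix which test decides it. The matter should be settled before the clinic codes are opened.

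**What to change.** Rewrite section 6.3 around one primary test of the between-arm contrast at clinic level, stating alpha, degrees of freedom and a 95% CI. Options:
- **Preferred:** regress clinic follow-up prevalence on arm and clinic baseline prevalence (t on 5 df).
- **Alternative:** an unpaired t-test of the eight clinic-level changes (6 df).
- **Support for either:** a permutation test over the C(8,4) = 70 allocations. Its smallest two-sided p is 2/70 = 0.029, so it can reach 5%.

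Use the same method for the last column of Tables 9 and 10. Report within-arm changes with confidence intervals and no p-values. Either describe the second and third steps or delete the reference to them.

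**Cost.** The change is to SAP wording, and the programming is simpler than the custom chi-square routine. The real cost is power. For 36% v 25% at follow-up, the pooled-ICC chi-square rejects about 91% of the time, but at a true alpha near 10%; the t-test on follow-up proportions has 81% at a true 5%. A test of change may have much less, or somewhat more, depending on a between-survey correlation that the SAP does not give (Step 5). Power for the baseline-adjusted regression was not calculated here. Section 3.5 should restate power for the contrast chosen, over a stated range of that correlation.

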6.4 Assumption checks

Post logistic regression derived residuals for pre and post analysis will be tested for normality using tests such as Shapiro-Francia, Kolmogorov-Smirnov test or the Skewness Kurtosis test. The F-ratio test will be used to test for equality of variances between the two groups being compared. Other model fit diagnostics will be performed to assess for outliers, leverage and influential data taking cognizance of the clustering.

6.5 Other analysis supporting the primary analysis (including sensitivity analyses)

Apart from looking at the observed effect of the intervention, a sensitivity analysis will be conducted:

- 1. The primary analysis on hypertensive drugs described in section 5.7 excludes from the analysis those who do not name any specific drugs we will include these in a sensitivity analysis.
- 2. We will undertake sensitivity with individuals analyzed in the "last" clinic that they attended.
- 3. We will adjust for potential confounding factors using the two stage regression model¹³. Firstly, two logistic regression models for control and intervention clinics that include covariates will be fitted separately, with individual level covariates such as gender and age. Secondly, based on residuals from the first stage we will aggregate outcomes to cluster level and cluster/clinic level factors (e.g. clinic size) will be used in regression modeling at the cluster level to test the effect of the intervention.
- 4. In order to compare the results from the two stage regression an alternative procedure will be used, the mixed effects model adjusting for covariates.

Model sensitivity to the individual-level data will be assessed on different temporal covariance structures (exchangeable, auto covariance and unstructured) on the final model. Such assessment will be made possible because of the many appointments with the 21 months of follow-up.

Thus, endeavors to ensure data are complete will be explored rigorously taking advantage of this longitudinal nature of data and, in the process a report for missing data

by variable will be compiled. This will help to classify the missing data as either missing at random (MAR) or missing not at random (MNAR). Assuming the data are MAR the proposed mixed logistic models should sufficiently handle these. If otherwise, as with MNAR we will employ data imputation procedures accordingly, taking caution not to distort the patterns observed from the data. However, as this is an area in which research is ongoing, this will be an exploratory analysis, not reported in the main trial report, and drawing on latest research. The dummy tables for these and details on how imputation on clustered data will be done, will not be provided in this analysis plan.

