4.2 Follow up

The follow-up survey will use a different sample, which will be selected using the same age/sex distribution. The data collection will be the same as that listed above for the baseline survey.

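### The two-stage adjusted analysis in SAP 6.5 fits stage one separately by arm, which removes the arm contrast before stage two tests it, except under a variant that the SAP does not state

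*SAP*

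**What the plan says.** Section 6.5 introduces its list as supporting work: "Apart from looking at the observed effect of the intervention, a sensitivity analysis will be conducted". Item 3 adjusts for confounding in two stages.

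- Stage one: "Firstly, two logistic regression models for control and intervention clinics that include covariates will be fitted separately". The covariates are measured on the person, and the examples given are sex and age. No survey (time) term is named, and the item does not say whether the baseline survey, the follow-up survey or both enter.
- Stage two: "Secondly, based on residuals from the first stage we will aggregate outcomes to cluster level". These values, together with clinic-level factors such as clinic size, "will be used in regression modeling at the cluster level to test the effect of the intervention".

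No step between the stages restores a comparison between arms. There is no common intercept, no common model and no standardisation of one arm to the other's model.

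Item 4 adds a covariate-adjusted mixed model for comparison with item 3. The paragraph after it says: "Model sensitivity to the individual-level data will be assessed on different temporal covariance structures (exchangeable, auto covariance and unstructured) on the final model". It justifies this by the many appointments over the 21 months of follow-up. On the surveys, section 4.2 says: "The follow-up survey will use a different sample, which will be selected using the same age/sex distribution".

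**The concern.** In a two-stage analysis, the arm effect must still be in the residuals when stage two looks for it. Stage one should therefore remove only what the covariates explain. A separate model for each arm has its own intercept, and that intercept absorbs the arm's overall level, including any effect of the intervention. The residuals then show how clinics differ from the average of their own arm and carry no comparison between arms.

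Items 3 and 4 are the only covariate-adjusted analyses of the intervention effect in 6.5, and only eight clinics are randomised, so an adjusted result will get attention. Followed to the letter under most readings, item 3 returns a null that comes from the method and says nothing about the trial. Section 7.1 analyses secondary outcomes as described for the primary outcome, so the wording may be carried over there too.

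**Working it through.** The SAP states no figure for this analysis, so there is none to reproduce. The check is algebra, then simulation.

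**Inputs from the SAP.** Eight clinics, four per arm (3.1); about 500 people per clinic per survey, background prevalence 36%, coefficient of variation 0.132, and a scenario of 36% against 21% (3.5). A difference of 11 points (36% against 25%) was also run.

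**Assumptions.** Two-sided 5% level (not stated in the SAP), age log-odds 0.3 per 10 years, sex log-odds 0.2, survey-specific clinic coefficient of variation 0.04. The algebra depends on none of these.

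**Algebra.** For a logistic model with an intercept, the score equation for the intercept is Σ(y − p̂) = 0 over the data fitted.

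1. *Separate fit, one survey.* The sum is zero in each arm. The size-weighted mean residual is zero in both arms, and so is their difference. With equal clinics the unweighted mean is zero as well. Without covariates, for 4 × 500 = 2,000 people per arm:
   - control: observed 0.36 × 2,000 = 720, expected 720
   - intervention: observed 0.21 × 2,000 = 420, expected 420
   - residual difference: 0 − 0 = 0, although the true difference is 15 points.
2. *Separate fit, both surveys with a survey term.* The survey term adds a second score equation, so residuals sum to zero within each survey in each arm. The change between surveys is then zero too.
3. *One common model without an arm term.* The fitted proportion is (720 + 420)/4,000 = 0.285. Residuals are 0.36 − 0.285 = +0.075 and 0.21 − 0.285 = −0.075, a difference of −0.15. The effect is kept.
4. *Separate fit, both surveys pooled, no survey term.* Suppose both arms start at 36%, control stays there and intervention falls to 21%, with equal survey sizes. The intervention model fits 0.285 in both surveys, and its residuals are +0.075 and −0.075. The change is −0.15 against 0 in control. The effect is recovered if the change is analysed. Follow-up residuals alone give −0.075, half of it.

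**Simulation.** 400 trials per scenario, age and sex as covariates, t-test on the eight clinic values. Entries are the mean residual difference between arms (or difference in change) and the rejection rate.

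| Stage one and what is analysed | Clinics | 36% v 25% | 36% v 21% |
|---|---|---|---|
| Separate by arm, follow-up | 500 each | 0.0000, 0% | 0.0000, 0% |
| Separate by arm, follow-up, unweighted | 250–800 | −0.0009, 0% | +0.0003, 0% |
| Separate by arm, both surveys with survey term, change | 250–800 | +0.0006, 0% | −0.0011, 0% |
| One common model, no arm term, follow-up | 500 each | −0.107, 77% | −0.144, 95% |
| One common model, no arm term, follow-up | 250–800 | −0.105, 78% | −0.148, 99% |
| Separate by arm, surveys pooled, no survey term, change | 250–800 | −0.106, 93% | −0.148, 99.5% |
| Same fit, follow-up residuals only | 250–800 | −0.054, 25% | −0.073, 55% |

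With unequal clinics and unweighted means, single trials under the separate fit ranged within about ±0.06. Size-weighted, they were exactly zero. Observed/expected ratios in place of differences gave the same picture: mean log ratio about 0, 0% rejection. With no true effect, the separate fit also rejected in 0%, while the common model rejected in 3% (equal clinics) and 6% (unequal), close to the nominal 5%.

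**The case against.** **The outcome is a change.** The primary outcome is the change between two surveys (2.2.1, 6.1), section 6.4 speaks of residuals for pre and post analysis, and item 3 names no survey term. A reader can fit each arm's model to both surveys pooled and compare the change in clinic residuals, and that works (step 4 of the check). This stands. A reader might infer that item 3 returns zero under every reading, and the documents do not support that. But the SAP does not state the working variant either, and the result runs from zero to the full effect depending on a choice it leaves open.

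**Zero is not always exact.** This stands too. With unequal clinics and unweighted means, the estimate is noise around zero.

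**It is only a sensitivity analysis.** Correct. A reader might infer that the main result is at risk, but the primary test is the ICC-adjusted chi-square in 6.3, which does not use these residuals. Item 4 would probably show a discrepancy. How readers would take an adjusted null is a prediction, and nothing in the documents settles it.

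**The SAP cites a textbook for the two-stage method.** An analyst might follow the source instead. The SAP's own sentence is nevertheless what is pre-specified, and it says two models fitted separately.

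**Item 4 and the temporal covariance structures.** A reader might infer that these structures cannot be fitted, or that the mixed model has inflated type I error. Neither is supported. The SAP bases the structures on repeated appointments, which are clinic-link visit data with every visit recorded (4.5, 5.8), and they can be fitted there. It gives no random-effects structure for the mixed model, so no error rate can be attached to it. What remains is narrower: the paragraph stands under a heading on the primary outcome, which comes from two surveys of different samples and is not planned as a repeated measure on a person.

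**Conclusion.** The point holds for item 3. With separate models by arm, fitted to one survey or to both surveys with a survey term, the arm contrast is removed before stage two. It is exactly zero for equal-sized or size-weighted clinics, and otherwise centred on zero with 0% rejection in simulation, even for the 15-point difference in 3.5. Clinic-level covariates in stage two cannot bring back information that sits in the stage-one intercepts. The algebra needs no assumption beyond an intercept in each model and residuals taken as observed minus expected. The rejection rates rest on the assumed covariate effects and the 5% two-sided level.

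The reach is limited to this pre-specified adjusted sensitivity analysis, and to secondary outcomes if the wording is carried over. The wording should be changed because it prescribes a spurious null under most readings and the correction is small.

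**What to change.** Replace the stage-one and stage-two sentences of item 3 with, for example:

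> One logistic model will be fitted to all eight clinics together (follow-up survey, or both surveys with a survey term), with the individual-level covariates and without an intervention term. Observed minus expected will be computed for each clinic, or its change between surveys. These eight values will be regressed on arm, with residual degrees of freedom equal to 6 minus the number of clinic-level covariates included (for example 5 with clinic size).

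The SAP should name one of the two options. The change between surveys matches the primary outcome as 6.1 defines it. The degrees of freedom follow from 8 clinics − 2 parameters (intercept and arm) = 6, less one for each clinic-level factor that item 3 already allows.

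In the paragraph after item 4, add that the temporal covariance structures apply only to repeated clinic-link visit data and not to the survey-based primary outcome.

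Cost: a few sentences of SAP text and a small change to the analysis program. No new data are needed.
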